11.1. Definition

1) Adverse Events (AEs)

Adverse events are undesirable medical occurrence in subjects administered a pharmaceutical product in clinical trials, and which does not necessarily have a causal relationship with the drugs. An adverse event(AE) can therefore be any unfavourable and unintended sign (including an abnormal laboratory finding), symptoms or diseases temporarily associated with the use of medicinal (investigational) product, whether or not related to the medicinal(investigational) product.

Adverse events may include not only those newly occurring after the participation in the research, but also worsened severity or frequencies compared to the initial evaluation, as well as abnormal diagnostic test results including abnormal laboratory findings.

2) Serious Adverse Events (SAEs)

In this study, SAE is defined as any untoward medical occurrence that:

- ① Results in death during the study
- ② Is life-threatening
- ③ Results in a persistent or significant disability/incapacity
- ④ Results in congenital anomaly/birth defect
- ⑤ Results in inpatient hospitalization or prolongation of existing hospitalization

In addition to the situations stated above, medical and scientific judgments will be made to determine whether the prompt reports are suitable. For example, an AE that may place the subject in danger, or that needs treatment to prevent worsening from the situations stated above, or that is regarded as having significant clinical influence by the investigator's decision, will be regarded as a SAE although it is not life-threatening or does not result in death or hospitalization.

3) Unlisted (Unexpected) Adverse Event

Unexpected Adverse Events refer to AEs in which the nature or severity is different compared to the information of approved package insert.

4) Relationship to the Study Drug

The definition of relationship is as follows.

- ① Not related: Adverse Event having no relationship with use of study drug
- ② Unlikely (Doubtful): Adverse events whose relationship to study drug makes a temporary causal relationship or improbable and in which other concomitant medications or underlying disease provides plausible explanations

- ③ Possible: Adverse events may be due to the use of the study drug. Other explanations, such as other concomitant medications or underlying diseases, are not conclusive. As the temporal relationship is reasonable, the causal relationship cannot be excluded.
- ④ Probable: Adverse events may be due to the use of the study drug. The temporal relationship is reasonable (e.g., confirmed by drug discontinuation) and does not appear to be due to concomitant medications or underlying diseases.
- ⑤ Definite: Adverse event is described as a possible adverse reaction and cannot be explained as a concomitant drug or a underlying disease. The temporal relationship is very plausible (e.g., confirmed by stopping and re-administering the study drug).

The Adverse Event will be judged to be related to the use of the study drug when the contribution of the drug to adverse event is Possible, Probable or Definite according to the above definition.

5) Grading for Severity

The severity of AE will be determined using CTCAE Version 4.0.

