11.2. Adverse Event Collection and Reporting

1) All Adverse Events(AEs)

All AEs found in subjects who received the study drugs from baseline visit or after the randomization will be collected. Any AEs that falls within the definition of a serious adverse event(SAE) will be reported as SAE regardless of specific evaluation items in the protocol.

All AEs regardless of the severity, seriousness, or relationship to the study drug, will be documented on source document (SD) and case report form (CRF) using English medical terms. When possible, if the signs and symptoms are due to common diseases (e.g., cough, runny nose, sneezing, laryngopharyngitis, stuffy head, will be reported as “upper respiratory infection”), it will be recorded using its diagnostic name in principle. The investigator will record his/her opinion of the relationship of AE to the study drugs on both SD and CRF, and record all evaluations necessary for management of AE on SD and report according to the regulations.

2) Serious Adverse Events (SAEs)

The investigator will report all SAEs that occur during the study in a timely manner according to the regulations of their respective IRB.

All SAEs that are not recovered by the end of the study or not resolved due to withdrawal from the study will be followed-up until the following instances.

- ① Recovery of AE
- ② Stabilization of AE

Confidential

MDR-END v14.0, 20Mar2020

- ③ When there are baseline evaluations, until restoration to the baseline status
- ④ When judged to be due to drugs other than the study drug or factors other than the study intervention
- ⑤ When there is a high possibility of not being able to receive additional information (when the subject or health manager denies giving additional information or when follow-up is not possible despite attempts)

Deaths of subjects during clinical trials will be judged as a SAE regardless of relationship to the study drug or whether or not being expected.

Requiring hospitalization (or prolongation of hospitalization) during the study will also be reported as a SAE, except for hospitalization in the following cases:

- ① Hospitalization scheduled for the study
- ② Hospitalization for social reasons without having AE
- ③ Elective operations or procedures scheduled prior to participation in the study (must be recorded in the case report form (CRF))

3) Pregnancy

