3.1 General Principle of Result Analysis

Data obtained from subjects through clinical trial will be analyzed by mITT (modified Intention-To-Treatment) analysis and PP (Per-Protocol) analysis. Efficacy evaluation will be based on a mITT (modified Intention-To-Treatment) and additional analysis on PP (Per-Protocol) group. Safety analysis will be performed on mITT, PP and the safety group (study drug administration group).

Subject Group	Definition
mITT	
- The mITT group includes participants who are randomized after satisfying eligibility criteria and receive study drugs at least one time. The subjects are not confirmed to be additionally resistant to fluoroquinolone, mono-resistant to rifampicin, or susceptible to rifampicin.

PP	
The PP (Per-Protocol) group includes participants that satisfy the following among the mITT group.
 
When completing over 80% of the planned treatment
 
: For control arm, 64 weeks or longer treatment; For investigational arm, 32 weeks or longer treatment in the 9-month treatment group and 42 weeks or longer treatment in the 12-month treatment group

Safety	
Participants who completed the study per protocol during the clinical trial period
 
: More than 80% of the planned period before treatment is completed, the following cases are considered protocol violation and excluded from the analysis group
 
① withdrawal or death.② The sputum test before culture conversion was not conducted③ Administration of study drug in the control arm 
The Safety analysis group includes participants who have taken study drugs at least one time.
 
: Evaluation based on the administration of study drug (delamanid or linezolid)

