3.7 Safety Analysis

The safety analysis evaluates subjects enrolled in this clinical trial and administered the study drug at least one time.

1) Adverse Events

- The analysis obtains the 95% confidence interval of the proportion of the subjects who have experienced one or more adverse event within each arm and performs the Chi-Square Test or Fisher's Exact Test to compare the treatment groups.
- It compares the occurrence rate of adverse drug reactions of the two arms using the Chi-square test or Fisher's exact test.
- It summarizes the number of adverse events of each arm.
- It summaries the number of expressions of five items (seriousness, severity, relation, action taken, and outcome) for each arm.
- The classification of adverse events by body system is organized according to the SOC (System Organ Class) and PT (Preferred Term) of MedDRA system.
- It describes the details such as demographic information, event date, end date, severity, relation, action taken, and outcome for the subjects who reveal serious adverse events.

2) Physical/Neurological Examination Result

- For the results of the physical/neurological examination, the analysis presents the proportion of subjects who were normal in screening visit (Visit1) and changed to abnormal at the final visit.

3) Chemistry/Electrolyte/Complete Blood Count Result

- The analysis presents the proportion of subjects who showed the chemistry/electrolyte/complete blood count result of "Normal" or "Abnormal NCS" at the baseline visit (Visit2) and changed to "Abnormal CS" at the final visit.

4) Concomitant Medication

- The analysis classifies the concomitant medication using the ATC (Anatomical Therapeutic Chemical)

Code presents it for each arm.

4. Subjects

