6.1 Adverse Events

The analysis presents the summary of the total number of adverse events, the number of subjects experiencing adverse events, and the serious adverse events, adverse event with grade 3-5 in this clinical trial (Table 23).

Table 23. Summary of Adverse Event Reported during Study Period

	Investigational Arm N=xx	Control Arm N=xx	Total N=xx
mITT			
Number of subjects showing adverse events, n (%)	xx (xx.xx)	xx (xx.xx)	xx (xx.xx)
95% confidence interval of adverse event rate	xx.xx±xx.xx	xx.xx±xx.xx	xx.xx±xx.xx
p-value ¹⁾	0.xxxx †† or **		
Number of adverse events, n	xx	xx	xx
Adverse drug reaction ²⁾			
Number of subjects showing adverse drug reaction, n (%)	xx (xx.xx)	xx (xx.xx)	xx (xx.xx)
p-value ³⁾	0.xxxx †† or **		
Number of adverse drug reaction, n	xx	xx	xx
Serious adverse events			

Number of subjects showing serious adverse events, n (%)	xx (xx.xx)	xx (xx.xx)	xx (xx.xx)
p-value ⁴⁾	0.xxxx †† or **		
Number of adverse events, n	xx	xx	xx
Adverse event of grade 3-5			
Number of subjects showing over grade 3 of adverse event, n (%)	xx (xx.xx)	xx (xx.xx)	xx (xx.xx)
p-value ⁵⁾	0.xxxx †† or **		
Number of grade 3 of adverse event, n	xx	xx	xx
Death			
Death, n (%)	xx (xx.xx)	xx (xx.xx)	xx (xx.xx)
p-value ⁶⁾	0.xxxx †† or **		
Seriousness			
Not serious, n	xx	xx	xx
Serious, n	xx	xx	xx
Severity			
Mild, n	xx	xx	xx
Moderate, n	xx	xx	xx
Severe, n	xx	xx	xx
life threatening or disabling, n	xx	xx	xx
Death, n	xx	xx	xx
Relation			
not related, n	xx	xx	xx
doubtful, n	xx	xx	xx
possible, n	xx	xx	xx
probable, n	xx	xx	xx

definite, n	xx	xx	xx
Action taken			
No action taken, n	xx	xx	xx
Dosage Adjustment of study drug, n	xx	xx	xx
Suspension of study drug, n	xx	xx	xx
Permanent termination of study drug, n	xx	xx	xx
Unknown, n	xx	xx	xx
Not applicable, n	xx	xx	xx
Dosage adjustment of TB medication other than the study drug, n	xx	xx	xx
Suspension of TB medication other than the study drug, n	xx	xx	xx
Permanent termination of TB medication other than the study drug, n	xx	xx	xx
Outcome			
Resolved, n	xx	xx	xx
Resolved with residual effect, n	xx	xx	xx
Ongoing, n	xx	xx	xx
Death, n	xx	xx	xx
Unknown, n	xx	xx	xx
PP	N=xx	N=xx	N=xx
Number of subjects showing adverse event, n (%)	xx (xx.xx)	xx (xx.xx)	xx (xx.xx)
95% confidence interval of adverse event rate	[xx.xx, xx.xx]	[xx.xx, xx.xx]	[xx.xx, xx.xx]
p-value ¹⁾	0.xxxx †† or **		xx
Number of adverse events, n	xx	xx	xx
Adverse drug reaction ²⁾			

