Severity			
Mild, n	xx	xx	xx
Moderate, n	xx	xx	xx
Severe, n	xx	xx	xx

life threatening or disabling, n	xx	xx	xx
Death, n	xx	xx	xx
Relation			
not related, n	xx	xx	xx
doubtful, n	xx	xx	xx
possible, n	xx	xx	xx
probable, n	xx	xx	xx
definite, n	xx	xx	xx
Action taken			
No action taken, n	xx	xx	xx
Dosage Adjustment of study drug, n	xx	xx	xx
Suspension of study drug, n	xx	xx	xx
Permanent termination of study drug, n	xx	xx	xx
Unknown, n	xx	xx	xx
Not applicable, n	xx	xx	xx
Dosage adjustment of TB medication other than the study drug, n	xx	xx	xx
Suspension of TB medication other than the study drug, n	xx	xx	xx
Permanent termination of TB medication other than the study drug, n	xx	xx	xx
Outcome			
Resolved, n	xx	xx	xx
Resolved with residual effect, n	xx	xx	xx
Ongoing, n	xx	xx	xx
Death, n	xx	xx	xx
Unknown, n	xx	xx	xx

†† p-value by the Chi-square test ** p-value by the Fisher's exact test

1) p-value for comparison test of adverse reaction incidence rate between groups

2) In the case of an adverse reaction related to the drug used, the contribution of the drug is Possible, Probable, or Definite

3) p-value for comparison test of the incidence of adverse drug reactions between groups

4) p-value for comparison test of incidence of serious adverse events between groups

5) p-value for the comparison test for the incidence of grade 3 adverse events between groups

6) p-value for intergroup mortality comparison test

The analysis presents the adverse events occurring for each body system during the clinical trial period. The body system is classified according to SOC (System Organ Class) and PT (Preferred Term) of the MedDRA system. The adverse events are summarized for each severity of the body system, relation, and body system (Tables 24, 25, and 26).

Table 24. Adverse Events for Each Body System

		Investigational Arm (N=xx)	Control Arm (N=xx)	Total (N=xx)
mITT				
System Organ Class	Preferred Term			
SOC1		X	X	X
	XXX	X	X	X
	XXX	X	X	X
SOC2		X	X	X
	XXX	X	X	X
	XXX	X	X	X
PP				
System Organ Class		Preferred Term		

SOC1	X	X	X	
	XXX	X	X	
	XXX	X	X	
SOC2	X	X	X	
	XXX	X	X	
	XXX	X	X	
Safety				
System Organ Class	Preferred Term			
SOC1	X	X	X	
	XXX	X	X	
	XXX	X	X	
SOC2	X	X	X	
	XXX	X	X	
	XXX	X	X	

Table 25. Adverse Events for Each Severity of Body System

System Organ Class	Preferred Term	Investigational Arm (N=xx)						Control Arm (N=xx)					
		Severity						Severity					
		1	2	3	4	5	>=3	1	2	3	4	5	>=3
mITT													
SOC1		X	X	X	X	X	X	X	X	X	X	X	X

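### Causality is recorded only against an undefined 'study drug'; on the one meaning the documents spell out (delamanid or linezolid), the between-arm adverse drug reaction test undercounts control-arm reactions

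*Combined protocol and SAP*

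**What the plan says.** Protocol 11.1, item 4, grades causality on five levels, from not related to definite, with the study drug as the reference. An event is graded unlikely where "other concomitant medications or underlying disease provides plausible explanations". The closing rule counts the top three grades as related and names the same reference: "The Adverse Event will be judged to be related to the use of the study drug when the contribution of the drug to adverse event". Protocol 11.2 carries this to the data: "The investigator will record his/her opinion of the relationship of AE to the study drugs on both SD and CRF". No item for relationship to other anti-TB drugs is described.

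SAP 3.7 uses the judgement for inference: "It compares the occurrence rate of adverse drug reactions of the two arms", by chi-square or Fisher's exact test. Table 23 (SAP 6.1) has a row and a p-value for it in each analysis group. Footnote 2 of that table gives the definition: "In the case of an adverse reaction related to the drug used, the contribution of the drug is Possible, Probable, or Definite".

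Study drug is used in two ways:

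- **Narrow.** Protocol 5.1.1, headed Study Drug, lists only linezolid and delamanid. SAP 3.1 says of the safety group "Evaluation based on the administration of study drug (delamanid or linezolid"), and SAP 6 repeats that gloss. SAP 3.1 treats study drug given in the control arm as a protocol violation. The action-taken rows of Table 23 have separate entries such as "Dosage adjustment of TB medication other than the study drug".
- **Broad.** The mITT rule in protocol 10.2 and SAP 3.1 requires participants in both arms to "receive study drugs at least one time". Footnote 4 of the control-arm schedule (protocol 7.1) speaks of giving study drugs. SAP 4.4 reports study-drug adherence for both arms, and its Table 14 has rows for levofloxacin, pyrazinamide and other drugs.

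**The concern.** The control arm takes an injectable-based regimen. Protocol 5.1.2 allows linezolid or delamanid there only in stated circumstances: injectable resistance, or strengthening the regimen after reactions to other drugs. If an investigator applies the causality scale with the spelled-out meaning, a reaction to an injectable or to cycloserine in a control participant who never took delamanid or linezolid is not related to study drug, and so is not an adverse drug reaction. Levofloxacin and pyrazinamide reactions in the investigational arm are lost in the same way, but that arm keeps its delamanid and linezolid reactions. The loss is therefore uneven between the arms.

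At stake is a planned p-value on tolerability in a trial whose rationale (protocol 1.2) rests partly on the toxicity of long second-line treatment. The error would make the new regimen look worse than it is. If sites read the term differently, the count would also depend on the site, in an open-label trial.

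**Working it through.** **Step 1: which meaning governs the causality field.** Protocol 11.1 and 11.2 use the term without defining it. The only explicit definitions or glosses (protocol 5.1.1, SAP 3.1, SAP 6) are narrow. Protocol 11.2 also contrasts the study drug with other drugs when it lists reasons for ending follow-up of a serious event. Table 23 gives other TB drugs their own action-taken rows but has a single relation block. Against this, footnote 2 refers to the drug used, and the mITT, schedule and adherence text needs the broad meaning. No section settles it.

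**Step 2: inputs for scale.**

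- The documents give no figure for the adverse drug reaction comparison. The only stated size is 48 per arm (protocol 10.1, SAP 2.3), or 102 after inflation. Unpooled check: (1.96 + 0.8416)² × (0.80×0.20 + 0.90×0.10) / (0.90 − 0.80 + 0.10)² = 7.849 × 0.25 / 0.04 = 49.06, close to 48. Inflation: 48 / (0.50 × 0.95) = 101.05, rounded up to 102.
- True reaction rate: 30% in both arms. This is an assumption, scaled on protocol 1.2, where 245 of 818 patients (29.95%) stopped drugs because of reactions.
- Test: two-sided 5% (SAP 3.6).
- Share of true reactions recorded as study-drug related in each arm: an assumption, varied below.

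**Step 3: false-positive chance.** The recorded rate in an arm is 30% × share recorded. With X and Y binomial at the two recorded rates, the joint probability is summed over every outcome at which the Pearson chi-square test rejects at 5%.

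| Share recorded, investigational / control | Recorded rates | 48 per arm | 102 per arm |
|---|---|---|---|
| 100% / 100% (regimen-based attribution) | 30% / 30% | 5.2% | 5.0% |
| 100% / 50% | 30% / 15% | 42.6% | 73.5% |
| 100% / 25% | 30% / 7.5% | 84.6% | 99.1% |
| 100% / 0% | 30% / 0% | about 100% | about 100% |
| 70% / 10% | 21% / 3% | 85.1% | 99.1% |

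The last row lets the investigational arm lose its levofloxacin and pyrazinamide reactions too. That loss alone does not restore balance. Fisher's exact test, the SAP's alternative, is more conservative but does not remove the inflation.

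**Step 4: as-treated split.** SAP 6 also divides the safety group by whether delamanid or linezolid was given. On the narrow meaning, the group given neither drug has no adverse drug reactions by construction.

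**The case against.** The strongest answer is that the narrow gloss is not a general definition. In SAP 3.1 it sits inside the safety-group entry, and in SAP 6 it serves an as-treated split. The definition attached to the tested row is footnote 2, which refers to the drug used. The control-arm schedule has an adverse drug reaction row from week 1 to end of treatment, so such data are planned for controls. Protocol 11.2 collects adverse events in those who received study drugs; read narrowly, that would leave most controls without any event collection, which cannot be intended. The CRF is not among the documents, so it may hold more than protocol 11.2 describes.

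Much of this stands, and it rules out three stronger readings that a reader might infer:

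- **That control reactions cannot count and the test is invalid.** This holds only on the narrow meaning, and the documents do not commit to it. Even then, some controls may receive delamanid or linezolid, so their count need not be zero.
- **That the mITT rule removes controls from the primary analysis.** The safety table in SAP 4.1 first removes participants given no study drug, then splits the rest into those with and without delamanid or linezolid. Tables 1 and 15 carry control-arm mITT counts. Controls are plainly meant to be included.
- **That controls could show at most 6%.** If 20% of controls were exposed (an assumption), 30% × 20% = 6% is an expected value. The ceiling is 20%, or about 10 of 51 (102 × 0.50 = 51). Against 15 of 51, Fisher's p is 0.36.

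What does not stand is that footnote 2 settles the matter. A table footnote cannot supply a judgement that the protocol did not clearly ask investigators to make.

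**Conclusion.** The point holds as an undefined reference drug feeding a stated between-arm test. On the documents' only explicit meaning, the adverse drug reaction comparison in SAP 3.7 and Table 23 is biased against the new regimen; on the broad meaning, the definition introduces no bias.

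The 43% and 85% figures illustrate the size on the narrow meaning and do not predict what will happen. They rest on an assumed equal true rate of 30%, full recording in the investigational arm, and a half or a quarter of control reactions recorded. The documents do not give the actual shares.

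The reach is limited. The all-event, serious-event, death and grade 3 or higher comparisons do not use causality and are unaffected, and grade 3 or higher events are the listed secondary safety outcome (protocol 5.3). The primary efficacy analysis is not touched.

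**What to change.** - In protocol 11.1 and 11.2, SAP 3.7 and Tables 23 and 26, define and record causality against any drug of the assigned anti-TB regimen, identically in both arms. Keep relationship to delamanid or linezolid as a separate item.
- Base footnote 2 of Table 23 on the regimen-level field.
- Where only delamanid or linezolid causality was captured, query it for the events concerned. Otherwise drop the between-arm adverse drug reaction p-value and rely on the all-cause and grade 3 or higher comparisons.
- As a wording alignment only, state mITT and safety entry in protocol 10.2 and SAP 3.1 as at least one dose of the assigned regimen.

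The cost is protocol and SAP wording, a CRF completion note, and either a causality query for events already entered or the loss of one supplementary p-value. No new procedures are needed.

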11.2. Adverse Event Collection and Reporting

1) All Adverse Events(AEs)

All AEs found in subjects who received the study drugs from baseline visit or after the randomization will be collected. Any AEs that falls within the definition of a serious adverse event(SAE) will be reported as SAE regardless of specific evaluation items in the protocol.

All AEs regardless of the severity, seriousness, or relationship to the study drug, will be documented on source document (SD) and case report form (CRF) using English medical terms. When possible, if the signs and symptoms are due to common diseases (e.g., cough, runny nose, sneezing, laryngopharyngitis, stuffy head, will be reported as “upper respiratory infection”), it will be recorded using its diagnostic name in principle. The investigator will record his/her opinion of the relationship of AE to the study drugs on both SD and CRF, and record all evaluations necessary for management of AE on SD and report according to the regulations.

2) Serious Adverse Events (SAEs)

The investigator will report all SAEs that occur during the study in a timely manner according to the regulations of their respective IRB.

All SAEs that are not recovered by the end of the study or not resolved due to withdrawal from the study will be followed-up until the following instances.

- ① Recovery of AE
- ② Stabilization of AE

Confidential

MDR-END v14.0, 20Mar2020

- ③ When there are baseline evaluations, until restoration to the baseline status
- ④ When judged to be due to drugs other than the study drug or factors other than the study intervention
- ⑤ When there is a high possibility of not being able to receive additional information (when the subject or health manager denies giving additional information or when follow-up is not possible despite attempts)

Deaths of subjects during clinical trials will be judged as a SAE regardless of relationship to the study drug or whether or not being expected.

Requiring hospitalization (or prolongation of hospitalization) during the study will also be reported as a SAE, except for hospitalization in the following cases:

- ① Hospitalization scheduled for the study
- ② Hospitalization for social reasons without having AE
- ③ Elective operations or procedures scheduled prior to participation in the study (must be recorded in the case report form (CRF))

3) Pregnancy

Pregnancy of subjects while on medication of the study drugs must be reported within 24 hours of awareness by the investigator. The investigator must complete a pregnancy notification form and submit it to the relevant person. Subjects who become pregnant while on medication of the study drugs must be withdrawn from the study immediately. Additional follow-up evaluation information is requested for side effects on newborns after giving birth as well as during pregnancy.

